6.6.17. Check and record concomitant medication/vaccination and intercurrent medical conditions

Concomitant medication/vaccination must be checked and recorded in the eCRF as described in [Section 7.6](#).

Intercurrent medical conditions must be checked and recorded in the eCRF as described in [Section 7.7](#).

6.6.18. Recording of AEs, SAEs, pregnancies and AEs of specific interest

- For subjects of the investigational vaccine groups (AduFx, 2PedFx, PedFx, Adu2Fx, and Adu1Fx)
 - Refer to Section 9.3 for procedures for the investigator to record AEs, SAEs, pregnancies and AEs of specific interest (meningitis and pIMDs). Refer to Section 9.4 for guidelines and how to report SAE, pregnancy and AEs of specific interest reports to GSK Biologicals.
 - The subjects will be instructed to contact the investigator immediately should they manifest any signs or symptoms they perceive as serious.
 - At each vaccination visit, diary cards will be provided to the subject. The subject will record body (oral) temperature and any solicited local/general AEs (i.e. on the day of vaccination and during the next six days) or any unsolicited AEs (i.e. on the day of vaccination and during the next 29 days) occurring after vaccination. The subject will be instructed to return the completed diary card to the investigator at the next study visit.
 - Collect and verify completed diary cards during discussion with the subject on Visit 3, Visit 6 and Visit 10 for subjects of AduFx, 2PedFx, PedFx, and Adu2Fx groups and on Visit 3 and Visit 10 for subjects of Adu1Fx groups.
 - Any unreturned diary cards will be sought from the subject through telephone call(s) or any other convenient procedure. The investigator will transcribe the collected information into the eCRF in English.
- For subjects of the infectivity controls group
 - Refer to Section 9.3 for procedures for the investigator to record AEs, SAEs and pregnancies. Refer to Section 9.4 for guidelines and how to report SAE and pregnancy reports to GSK Biologicals.
 - The subjects will be instructed to contact the investigator immediately should they manifest any signs or symptoms they perceive as serious.

6.6.19. Study conclusion

The investigator will:

- review data collected to ensure accuracy and completeness
- complete the Study Conclusion screen in the eCRF.

6.7. Biological sample handling and analysis

Please refer to the SPM for details on biospecimen management (handling, storage and shipment).

Samples will not be labeled with information that directly identifies the subject but will be coded with the identification number for the subject (subject number).

- Collected samples will be used for protocol mandated research and purposes related to the improvement, development and quality assurance of the laboratory tests described in this protocol. This may include the management of the quality of these tests, the maintenance or improvement of these tests, the development of new test methods, as well as making sure that new tests are comparable to previous methods and work reliably.
- It is also possible that future findings may make it desirable to use the samples acquired in this study for future research, not described in this protocol. Therefore, all subjects in countries where this is allowed, will be asked to give a specific consent to allow GSK or a contracted partner to use the samples for future research. Future research will be subject to the laws and regulations in the respective countries and will only be performed once an independent Ethics Committee or Review Board has approved this research.

Information on further investigations and their rationale can be obtained from GSK Biologicals.

Any sample testing will be done in line with the consent of the individual subject.

Refer also to the [Investigator Agreement](#), where it is noted that the investigator cannot perform any other biological assays except those described in the protocol or its amendment(s).

If additional testing is performed, the marker priority ranking given in Section 6.7.4 may be changed.

Collected samples will be stored for a maximum of 20 years (counting from when the last subject performed the last study visit), unless local rules, regulations or guidelines require different timeframes or different procedures, which will then be in line with the subject consent. These extra requirements need to be communicated formally to and discussed and agreed with GSK Biologicals.

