6.2. Subject identification and randomization of treatment

6.2.1. Subject identification

Subject identification numbers will be assigned sequentially to the subjects who have consented to participate in the study, according to the range of subject identification numbers allocated to the center.

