6.2.2.2.1. Study group and treatment number allocation

The target is to enroll approximately 150 subjects (26 subjects per vaccine group and between 20 and 30 subjects in the infectivity control group). Randomization will be performed on the investigational vaccine groups (AduFx, 2PedFx, PedFx, Adu2Fx, and Adu1Fx) and not for the infectivity controls. The first enrolled 130 subjects will be allocated to the vaccine groups (AduFx, 2PedFx, PedFx, Adu2Fx, and Adu1Fx) and the subsequent subjects will be allocated to the infectivity controls group.

Allocation of the subject to a study group at the investigator site will be performed using a randomization system on internet (SBIR). The randomization algorithm will use a minimization procedure accounting for center.

After obtaining the signed and dated ICF from the subject and having checked the eligibility of the subject, the site staff in charge of the vaccine administration will access SBIR. Upon providing the subject identification number, the randomization system will determine the study group and will provide the treatment number to be used for the first dose.

The number of each administered treatment must be recorded in the eCRF on the Vaccine Administration screen.

When SBIR is not available, please refer to the SBIR user guide or the Study Procedures Manual (SPM) for specific instructions.

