6.3. Method of blinding

This study is open label.

The laboratory in charge of the laboratory testing will be blinded to the treatment, and codes will be used to link the subject and study (without any link to the treatment attributed to the subject) to each sample.

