6.4.1.5. Management of infected human subjects

The pre-patent period for *P. falciparum* in man normally averages 9-12 days. In previous studies, the pre-patent period in controls varied from 7-18 days. The shortest reported pre-patent period in man is five days, and the longest is 25 days [Ballou, 1987]. An immunized individual who does not have complete protection may have a prolongation of the parasite pre-patent period.

Beginning on Day 5 (Day 291 [Visit 12]) after their challenge, subjects will be seen and evaluated daily by a study investigator and blood will be drawn for blood smears to check for the presence of parasites as described in Section 6.4.1.4. If fever or symptoms develop at any time, blood smears will be done more frequently (every 6 to 12 hours), and a study investigator will evaluate the subject. A confirmed positive result will be relayed immediately to the on-call investigator/study personnel by the microscopists. The infection will be treated early (i.e. as soon as parasites can be identified on thick smear) according to the treatment regimen outlined in Section 6.4.1.6.

Beginning on Day 9 post-challenge (Day 295 [Visit 16]), a group of hotel rooms in the local area of WRAIR, will be reserved for malaria-challenged subjects. The subjects will be required to spend their nights there to allow for more rapid assessment of any potential symptoms of malaria during the hours that the study centers are closed. There will be an investigator present on-site and available for subject assessment. There will also be qualified study personnel on site 24 hours per day during the hotel phase of the study.

A blood sample for assessment of parasitemia (PCR testing) will be collected on the day of subject entry into the hotel phase (Day 295 [Visit 16]) to provide the study team an estimate of the number of subjects likely to develop malaria within the first few days of the hotel phase. This will allow the principal investigator and the study team to maximize subject safety by properly allocating resources and medical personnel to meet any high demand periods (i.e. periods when a large number of subjects are/will become ill). These samples will be processed by and assessed at WRAIR.

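### Samples carry sequential subject numbers and all controls are enrolled last, so the protocol's own coding rule contradicts its laboratory blind for vaccine versus control

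*Protocol*

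**What the plan says.** Four provisions of the protocol bear on this point.

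- **Numbering (6.2.1).** "Subject identification numbers will be assigned sequentially to the subjects who have consented to participate in the study". The trial has one centre, so one number range applies.
- **Order of allocation (6.2.2.2.1).** "The first enrolled 130 subjects will be allocated to the vaccine groups", and "the subsequent subjects will be allocated to the infectivity controls group". Controls are not randomised.
- **Sample code (6.7).** Samples "will be coded with the identification number for the subject (subject number"). The sentence covers samples in general and does not name blood films. Handling details are left to the SPM.
- **Blinding (6.3).** The study is open label, but the testing laboratory is to be kept unaware of treatment. The means given is that "codes will be used to link the subject and study (without any link to the treatment attributed to the subject) to each sample".

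The primary endpoint is a human reading of thick films (6.4.1.4), and any parasite density above zero counts as infection (Section 4). Neither the protocol nor the SAP describes a separate slide code, a mixed reading order or a mandatory second reading of negative films.

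**The concern.** In an open-label trial, laboratory blinding is the only masking the protocol states. Here the three operational rules (numbering, allocation order, sample code) together undo the property that 6.3 claims. A microscopist who sees the subject number can tell a late-enrolled control from an early-enrolled vaccinee. The number does not reveal which vaccine arm a subject is in, because the arms are randomised within the first 130.

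If films do carry that number, a reader who expects controls to turn positive could search longer or call sooner in controls, and could discount a scanty film in a vaccinee. Both tendencies would favour the vaccine. The quantities at stake are vaccine efficacy (VE) against controls, the log-rank comparison of time to onset with controls (protocol 11.8, SAP 6.3.1), and the significance test for any schedule with little true protection. That last case matters because the trial's purpose is to test reduced and alternative schedules.

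**Working it through.** **Step 1: does number order follow group?**

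- Protocol 5.1 treats a signed consent form as enrolment, so numbers issued at consent follow enrolment order.
- Vaccinees: 5 × 26 = 130, screened from Day -90 to Day 0 (Tables 6 and 7).
- Controls: 20 to 30, screened from Day 230 to Day 286 (Table 8). This agrees with the 0 to 56 days before challenge in Table 11, since 286 − 230 = 56.
- Screen failures also use up numbers, so the boundary is not exactly at 130, but controls still come after vaccinees.

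Applied as written, 6.2.1, 6.2.2.2.1 and 6.7 give every control a higher number than every vaccinee. For this contrast the code carries the treatment link that 6.3 says it lacks.

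**Step 2: the plan's own power figure (protocol 11.4).** Inputs: 19/20 controls and 6/20 vaccinees positive, two-sided 5% Fisher exact test.

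- VE = 1 − (6/20)/(19/20) = 68.4%, against about 68% stated.
- Power by full enumeration with rates 0.95 and 0.30, n = 20 per group: 99.7%, against 99% stated.
- Overall power for five comparisons: 0.99^5 = 95.1%, against 96% stated. From the unrounded value it is 98.3% under independence, or 98.5% allowing for the shared controls.

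The stated power is reproduced and is not in dispute.

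**Step 3: how much misreading would change a conclusion?** Against 19/20 controls, 13/20 positive vaccinees gives p = 0.044 and 14/20 gives p = 0.091. With no true effect (19/20 in both groups), 19 − 13 = 6 infected vaccinees would have to be missed on every film through Day 28 after challenge.

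**Step 4: an illustration.** The documents give no misreading rate, so the rates below are assumptions. Each is the share of infected vaccinees missed throughout follow-up, with none missed in controls (control rate 0.95, n = 20 per group). Entries are the chance of p < 0.05.

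| True vaccinee rate | True VE | 0% missed | 10% missed | 20% missed |
|---|---|---|---|---|
| 0.95 | 0% | 0.2% | 6.2% | 27.1% |
| 0.80 | 15.8% | 16.8% | 38.7% | 61.6% |
| 0.65 | 31.6% | 58.9% | 74.9% | 86.7% |
| 0.30 (planned) | 68.4% | 99.7% | 99.8% | 99.9% |

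**Step 5: time to onset.** Films are daily from Day 291 to Day 304. Calling a scanty film one scheduled day later moves onset by one day. Against the 9 to 12 day average pre-patent period in 6.4.1.5, that is 1/12 = 8% to 1/9 = 11%. This shows the scale of one delayed call and does not estimate bias.

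**The case against.** The strongest reply is that no passage says what is written on a blood film. The sentence in 6.7 comes from a general statement about not identifying subjects directly, while 6.3 is the specific blinding provision. Slide preparation and reading follow laboratory procedures (Appendix A) and a validated microscopy procedure (6.4.1.4), and sampling details are in the SPM (6.6.16). None of these was available, and any of them could re-code films. This stands. A reader might infer that the microscopists were in fact unblinded, and the documents do not support that. They show only that the one coding rule given conflicts with the blind.

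A reader might also infer that the endpoint has no other safeguard. That is wrong. All films are archived for possible re-examination, and positives are confirmed before they are relayed (6.4.1.5). There are 14 + 5 = 19 scheduled smear days, with more frequent films if symptoms develop. For occurrence, one discounted film rarely makes a subject negative, because later films would have to be missed too. These safeguards protect time to onset less, and no routine check of negative films is described.

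Two further inferences should be resisted. The change in VE from reclassifying one subject is arithmetic on that subject, not an estimate of bias. And although 6.4.1.5 says of the Day 295 PCR samples that "These samples will be processed by and assessed at WRAIR", which is also where slides are read, a shared institution does not mean shared readers, and PCR does not reveal group.

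**Conclusion.** The contradiction between 6.3 and the combination of 6.2.1, 6.2.2.2.1 and 6.7 is real and should be resolved. It is confined to comparisons with the infectivity controls: the primary endpoint and time to onset versus controls. Comparisons with AduFx are not exposed by this route.

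The conclusion assumes that blood films follow the general coding rule in 6.7. If the SPM or the slide procedures already re-code them, only the protocol text needs correcting.

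The documents give no basis for a size of bias. At the planned effect the primary conclusion does not depend on this point. The exposure lies in time to onset, in the VE estimate, and in any weakly effective schedule, where the significance test is sensitive to modest misreading under the assumed rates above.

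**What to change.** In 6.3 and 6.7, state that blood-smear samples from Day 291 to Day 314 carry a challenge-phase code in place of the subject number. The code is drawn at random from one common list covering all six groups. The clinical team holds the key, and the on-call investigator can reach it at once, so that action on a positive film is not delayed.

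The cost is one extra label set, an SPM instruction, and a decoding step for each positive film. Sample size, visits and analysis do not change. If films are already re-coded, one sentence saying so in 6.3 and 6.7 is enough.

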6.7.1. Use of specified study materials

When materials are provided by GSK Biologicals, it is MANDATORY that all clinical samples (including serum samples) be collected and stored exclusively using those materials in the appropriate manner. The use of other materials could result in the exclusion of the subject from the ATP analysis (See Section 11.5 for the definition of cohorts to be analyzed). The investigator must ensure that his/her personnel and the laboratory(ies) under his/her supervision comply with this requirement. However, when GSK Biologicals does not provide material for collecting and storing clinical samples, appropriate materials from the investigator's site must be used. Refer to the Module on Clinical Trial Supplies in the SPM.

6.7.2. Biological samples

Details of the quantity of biological sample to be taken at each timepoint during the study are provided in [Table 12](#).

Table 12 Biological samples (whole blood)

Study Phase	Timepoint	Sample type	Total volume of blood per visit (ml)					Infectivity control
			AduFx	2PedFx	PedFx	Adu2Fx	Adu1Fx	
Pre-vaccination	Visit 1 (Screening)	Blood sampling for HIV, HCV and HBsAg	17.0 ml	17.0 ml	17.0 ml	17.0 ml	17.0 ml	-
		Blood sampling for hematology and biochemistry analysis	7.5 ml	7.5 ml	7.5 ml	7.5 ml	7.5 ml	-
		Total:	24.5 ml	24.5 ml	24.5 ml	24.5 ml	24.5 ml	-
	Visit 2 (Day 0)	Blood sampling for antibody determination and serum repository	20.0 ml	20.0 ml	20.0 ml	20.0 ml	20.0 ml	-
		Blood sampling for RNA sequencing	12.0 ml	12.0 ml	12.0 ml	12.0 ml	12.0 ml	-
		Blood sampling for PBMC and plasma repository	30.0 ml	30.0 ml	30.0 ml	30.0 ml	30.0 ml	-
Total:		62.0 ml	62.0 ml	62.0 ml	62.0 ml	62.0 ml	-	
Post-Dose 1	Visit 3 (Day 28)	Blood sampling for RNA sequencing	12.0 ml	12.0 ml	12.0 ml	12.0 ml	12.0 ml	-
		Blood sampling for PBMC and plasma repository	30.0 ml	30.0 ml	30.0 ml	30.0 ml	30.0 ml	-
		Total:	42.0 ml	42.0 ml	42.0 ml	42.0 ml	42.0 ml	-
Post-Dose 2* or Post-Dose 1**	Visit 4 (Day 29)	Blood sampling for RNA sequencing	12.0 ml	12.0 ml	12.0 ml	12.0 ml	-	-
		Total:	12.0 ml	12.0 ml	12.0 ml	12.0 ml	-	-
	Visit 5 (Day 35)	Blood sampling for PBMC and plasma repository	30.0 ml	30.0 ml	30.0 ml	30.0 ml	-	-
		Blood sampling for hematology and biochemistry analysis	7.5 ml	7.5 ml	7.5 ml	7.5 ml	-	-
		Total:	37.5 ml	37.5 ml	37.5 ml	37.5 ml	-	-
	Visit 6 (Day 58)	Blood sampling for antibody determination and serum repository	20.0 ml	20.0 ml	20.0 ml	20.0 ml	-	-
		Blood sampling for PBMC and plasma repository	30.0 ml	30.0 ml	30.0 ml	30.0 ml	-	-
		Blood sampling for hematology and biochemistry analysis	7.5 ml	7.5 ml	7.5 ml	7.5 ml	-	-
		Total:	57.5 ml	57.5 ml	57.5 ml	57.5 ml	-	-
	Visit 7 (Day 196)	Blood sampling for antibody determination and serum repository	20.0 ml	20.0 ml	20.0 ml	20.0 ml	20.0 ml	-
		Blood sampling for RNA sequencing	12.0 ml	12.0 ml	12.0 ml	12.0 ml	12.0 ml	-
		Blood sampling for PBMC and plasma repository	30.0 ml	30.0 ml	30.0 ml	30.0 ml	30.0 ml	-
Total:		62.0 ml	62.0 ml	62.0 ml	62.0 ml	62.0 ml	-	

CONFIDENTIAL

205081 (MALARIA-092)

Protocol Administrative Change 1 Final

Study Phase	Timepoint	Sample type	Total volume of blood per visit (ml)					Infectivity control	
			AduFx	2PedFx	PedFx	Adu2Fx	Adu1Fx		
Post-Dose 3* or Post-Dose 2**	Visit 8 (Day 197)	Blood sampling for RNA sequencing	12.0 ml	12.0 ml	12.0 ml	12.0 ml	12.0 ml	-	
		Total:	12.0 ml	12.0 ml	12.0 ml	12.0 ml	12.0 ml	12.0 ml	-
	Visit 9 (Day 203)	Blood sampling for PBMC and plasma repository	30.0 ml	30.0 ml	30.0 ml	30.0 ml	30.0 ml	-	
		Blood sampling for hematology and biochemistry analysis	7.5 ml	7.5 ml	7.5 ml	7.5 ml	7.5 ml	-	
	Total:	37.5 ml	37.5 ml	37.5 ml	37.5 ml	37.5 ml	37.5 ml	-	
	Visit 10 (Day 226)	Blood sampling for antibody determination and serum repository	20.0 ml	20.0 ml	20.0 ml	20.0 ml	20.0 ml	-	
		Blood sampling for PBMC and plasma repository	30.0 ml	30.0 ml	30.0 ml	30.0 ml	30.0 ml	-	
		Blood sampling for hematology and biochemistry analysis	7.5 ml	7.5 ml	7.5 ml	7.5 ml	7.5 ml	-	
		Total:	57.5 ml	57.5 ml	57.5 ml	57.5 ml	57.5 ml	57.5 ml	-
	Pre-challenge	Visit 1b (Screening)	Blood sampling for HIV, HCV and HBsAg	-	-	-	-	-	17.0 ml
			Blood sampling for hematology and biochemistry analysis	-	-	-	-	-	7.5 ml
			Total:	-	-	-	-	-	24.5 ml
Visit 11 (Day 286)		Blood sampling for antibody determination and serum repository	20.0 ml	20.0 ml	20.0 ml	20.0 ml	20.0 ml	-	
		Blood sampling for PBMC and plasma repository	30.0 ml	30.0 ml	30.0 ml	30.0 ml	30.0 ml	-	
		Total:	50.0 ml	50.0 ml	50.0 ml	50.0 ml	50.0 ml	50.0 ml	-
Post-challenge	Visit 12 (Day 291)	Blood sampling for assessment of parasitemia (blood smear)	2.0 ml	2.0 ml	2.0 ml	2.0 ml	2.0 ml	2.0 ml	
	Visit 13 (Day 292)	Blood sampling for assessment of parasitemia (blood smear)	2.0 ml	2.0 ml	2.0 ml	2.0 ml	2.0 ml	2.0 ml	
	Visit 14 (Day 293)	Blood sampling for assessment of parasitemia (blood smear)	2.0 ml	2.0 ml	2.0 ml	2.0 ml	2.0 ml	2.0 ml	
	Visit 15 (Day 294)	Blood sampling for assessment of parasitemia (blood smear)	2.0 ml	2.0 ml	2.0 ml	2.0 ml	2.0 ml	2.0 ml	
	Visit 16 (Day 295)	Blood sampling for assessment of parasitemia (blood smear)	2.0 ml	2.0 ml	2.0 ml	2.0 ml	2.0 ml	2.0 ml	
		Blood sampling for assessment of parasitemia at start of hotel phase (PCR)****	2.0 ml	2.0 ml	2.0 ml	2.0 ml	2.0 ml	2.0 ml	
	Visit 17 (Day 296)	Blood sampling for assessment of parasitemia (blood smear)	2.0 ml	2.0 ml	2.0 ml	2.0 ml	2.0 ml	2.0 ml	
	Visit 18 (Day 297)	Blood sampling for assessment of parasitemia (blood smear)	2.0 ml	2.0 ml	2.0 ml	2.0 ml	2.0 ml	2.0 ml	
	Visit 19 (Day 298)	Blood sampling for assessment of parasitemia (blood smear)	2.0 ml	2.0 ml	2.0 ml	2.0 ml	2.0 ml	2.0 ml	
	Visit 20 (Day 299)	Blood sampling for assessment of parasitemia (blood smear)	2.0 ml	2.0 ml	2.0 ml	2.0 ml	2.0 ml	2.0 ml	
	Visit 21 (Day 300)	Blood sampling for assessment of parasitemia (blood smear)	2.0 ml	2.0 ml	2.0 ml	2.0 ml	2.0 ml	2.0 ml	
	Visit 22 (Day 301)	Blood sampling for assessment of parasitemia (blood smear)	2.0 ml	2.0 ml	2.0 ml	2.0 ml	2.0 ml	2.0 ml	
	Visit 23 (Day 302)	Blood sampling for assessment of parasitemia (blood smear)	2.0 ml	2.0 ml	2.0 ml	2.0 ml	2.0 ml	2.0 ml	
	Visit 24 (Day 303)	Blood sampling for assessment of parasitemia (blood smear)	2.0 ml	2.0 ml	2.0 ml	2.0 ml	2.0 ml	2.0 ml	

CONFIDENTIAL

205081 (MALARIA-092)

Protocol Administrative Change 1 Final

Study Phase	Timepoint	Sample type	Total volume of blood per visit (ml)					
			AduFx	2PedFx	PedFx	Adu2Fx	Adu1Fx	Infectivity control
	Visit 25 (Day 304)	Blood sampling for assessment of parasitemia (blood smear)v	2.0 ml	2.0 ml	2.0 ml	2.0 ml	2.0 ml	2.0 ml
	Visit 26 (Day 306)	Blood sampling for assessment of parasitemia (blood smear)	2.0 ml	2.0 ml	2.0 ml	2.0 ml	2.0 ml	2.0 ml
	Visit 27 (Day 308)	Blood sampling for assessment of parasitemia (blood smear)	2.0 ml	2.0 ml	2.0 ml	2.0 ml	2.0 ml	2.0 ml
	Visit 28 (Day 310)	Blood sampling for assessment of parasitemia (blood smear)	2.0 ml	2.0 ml	2.0 ml	2.0 ml	2.0 ml	2.0 ml
	Visit 29 (Day 312)	Blood sampling for assessment of parasitemia (blood smear)	2.0 ml	2.0 ml	2.0 ml	2.0 ml	2.0 ml	2.0 ml
	Visit 30 (Day 314)	Blood sampling for assessment of parasitemia (blood smear)	2.0 ml	2.0 ml	2.0 ml	2.0 ml	2.0 ml	2.0 ml
		Blood sampling for antibody determination and serum repository	20.0 ml	20.0 ml	20.0 ml	20.0 ml	20.0 ml	-
		Blood sampling for hematology and biochemistry analysis	7.5 ml	7.5 ml	7.5 ml	7.5 ml	7.5 ml	7.5 ml
		Total:	29.5 ml	31.5 ml	31.5 ml	31.5 ml	31.5 ml	9.5 ml
	Visit Par***	Blood sampling for hematology and biochemistry analysis	7.5 ml	7.5 ml	7.5 ml	7.5 ml	7.5 ml	7.5 ml
			Total:	7.5 ml				
Study end	Visit 31 (Day 376)	Blood sampling for antibody determination and serum repository	20.0 ml	20.0 ml	20.0 ml	20.0 ml	20.0 ml	-
		Blood sampling for PBMC and plasma repository	30.0 ml	30.0 ml	30.0 ml	30.0 ml	30.0 ml	-
		Total:	50.0 ml	50.0 ml	50.0 ml	50.0 ml	50.0 ml	-
		Total blood collected over the entire study:	579.5 ml	579.5 ml	579.5 ml	579.5 ml	472.5 ml	79.5 ml

* For groups AduFx, 2PedFx, PedFx and Adu2Fx.

** For group Adu1Fx.

*** Biochemistry and hematology parameters will be collected the day of first parasitemia (between Visit 12 [Day 291] and Visit 29 [Day 312]).

**** Blood sample for assessment of parasitemia by PCR will be collected on the day of subject entry into the hotel (Day 295 [Visit 16]).

